## 3.3. Computing Environment

All descriptive statistical analyses will be performed using SAS v9.4 or later unless otherwise noted. Medical history and AEs will be coded using MedDRA v20.0. Concomitant medications will be coded using the World Health Organization (WHO) Drug Dictionary March 2017

21

#### 3.4. Baseline Definitions

For all analyses, baseline will be defined as the most recent measurement prior to the first administration of study drug. The day of first dose of study medication is Day 0 in the Schedule of Assessments (SOA) and will be considered Relative Study Day 1.

### 3.5. Methods of Pooling Data

Subjects will be pooled across all sites. Data will be presented by treatment group and overall.

### 3.6. Adjustments for Covariates

No formal statistical analyses that adjust for possible covariate effects are planned.

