4 ENDPOINTS

4.1 Safety & tolerability:

• Safety and tolerability endpoints will consist of all adverse events reporting during the study duration.

4.2 Efficacy:

Difference in Atopic Dermatitis Area Severity Index (EASI) Score from Baseline to Day 28

4.3 Exploratory:

- Difference in Visual Analog Scale (VAS) Score for Pruritus from Baseline to Day 28
- Difference in the Skindex 16 Score from Baseline to Day 28
- Difference in the IGA score from Baseline to Day 28
- Difference in Actigraphy Movement Count per Hour and sleep quality during the night from Baseline to Day 28
- Difference in biomarkers between active and vehicle groups
- Composition of microbiome
- Difference in skin microbiota from baseline to Day 28 between active and vehicle groups
 - Observing a difference in Staphylococcus aureus and a more diverse microbial collection on the patient's skin.

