15.4.5 Efficacy Analyses

All efficacy analyses will be performed on the ITT population and PP population. P-values from analyses of efficacy endpoints must be interpreted in an exploratory fashion since there is no adjustment for multiple endpoints in this study.

The EASI score and other continuous efficacy endpoints will be summarized using descriptive statistics at Baseline, Day 14, Day 28 and Day 42 for actual values and change-from-baseline values. The difference in treatment groups in change-from-baseline values at post-baseline visits will be analyzed using a mixed Analysis of Variance with one between-subject variable (active group vs. vehicle group) and one within-subject variable (Baseline vs. Day 14, Day 28, Day 42). The interaction between within-subject and between-subject variable will be included in the mixed model to test if any difference in treatment groups at post-baseline visits. Outputs from the analysis will include the p-value for the treatment group and interaction factor separately. The p-value should be evaluated at a significance level of 0.05.

Additionally, a one-sided two-sample equal-variance t-test will be performed as a supportive test to analyze the differences in treatment group means in change from baseline at each post-baseline visit (Day 14, Day 28, Day 42). Output from the analysis will include a 95% confidence interval for the difference in treatment groups means at each visit, and the p-values from the hypothesis test of no difference in treatment group means at each visit. The p-value should be evaluated at a one-sided significance level of 0.025.

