#### 4.3.1. EASI, IGA, VAS

EASI, IGA, and VAS scores will be summarized using descriptive statistics at Baseline, Day 14, Day 28, and Day 42 for actual values and change-from-baseline values. Tabulations will be produced for both the ITT and PP populations.

The difference in treatment groups in change-from-baseline values at post-baseline visits will be analyzed using a mixed model Analysis of Variance with one between-subject variable (active group vs. vehicle group) and one within-subject variable (Day 14, Day 28, and Day 42).

The interaction between within-subject and between-subject variable will be included in the mixed model to test if any difference in treatment groups at post-baseline visits.

The model will include treatment group, siteid and visit as the independent effects and the interaction term treatment group\*visit\*siteid. Outputs from the analysis will include the p-value

for the treatment group and interaction factor separately. The p-value should be evaluated at a significance level of 0.05.

Mixed model ANOVA will be implemented using PROC GLM in SAS using the REPEATED option.

Additionally, a one-sided two-sample equal-variance t-test will be performed as a supportive test to analyze the differences in mean change in scores from baseline between treatment groups at each post baseline visit (Day 14, Day 28, Day 42). Output from the analysis will include a one sided 95% confidence interval and p-value. The p-value should be evaluated at a one-sided significance level of 0.025.

The above analysis will also be performed by subgroups – age, gender, and race for the ITT Population.

An exploratory analysis will also be conducted by the number of AD sites (1, 2 and >2) the subjects had.

At each visit, based on the score, subjects will be categorized into the below categories.

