#### 4.3.2. Skindex 16 score:

The Skindex 16 score – average of all 16 items in the scale will be summarized using descriptive statistics at Baseline, Day 14, Day 28, and Day 42 for actual values and change-from-baseline values for both ITT and PP populations.

The three subscores – Symptom subscale (average of items 1-4), Emotional subscale (average of items 5 -11), Functional subscale (average of items 12 -16) will also be summarized similarly.

The difference in treatment groups in change-from-baseline values at post-baseline visits will be analyzed using a mixed model Analysis of Variance similar to as described for the EASI score. The above analysis will also be performed by subgroups - age, race, and gender for the ITT population.

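### The change-score analyses of EASI, IGA, VAS and Skindex 16 are valid but leave out the baseline score; adding it is a nearly free, probably small, gain in precision

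*SAP*

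**What the plan says.** SAP 3.6: "No formal statistical analyses that adjust for possible covariate effects are planned". SAP 4.3.1 gives the model for change from baseline in EASI, IGA and VAS: "The model will include treatment group, siteid and visit as the independent effects and the interaction term treatment group" by visit by siteid. Baseline is not among the terms. On software: "Mixed model ANOVA will be implemented using PROC GLM in SAS using the REPEATED option". A one-sided two-sample t-test at each visit, also without baseline, "will be performed as a supportive test to analyze the differences in mean change in scores from baseline". For Skindex 16, SAP 4.3.2 says the change scores will be "analyzed using a mixed model Analysis of Variance similar to as described for the EASI score".

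Protocol 15.4.5 plans treatment, visit and their interaction ("The interaction between within-subject and between-subject variable will be included in the mixed model"), has no site term, and lists Baseline as a level of the within-subject factor. It also asks for a 95% confidence interval. The SAP drops the Baseline level, adds siteid terms and asks for a one-sided 95% interval. SAP section 5 lists only the per-protocol definition and the deferral of biomarker and microbial data.

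On the status of the results, protocol 15.4.5 says that efficacy p-values "must be interpreted in an exploratory fashion since there is no adjustment for multiple endpoints in this study". Protocol 4.2 defines the EASI endpoint as "Difference in Atopic Dermatitis Area Severity Index (EASI) Score from Baseline to Day 28". The SAP tests three visits and does not say which one is the main EASI result.

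**The concern.** Subtracting baseline removes its influence only if follow-up rises one-for-one with baseline, so that the slope of change on baseline is 0. Measurement error and within-patient variation make a follow-up slope below 1 plausible for all four scores. The change score then still carries baseline variation. That variation widens the interval, and a chance baseline imbalance between arms moves the estimate. The baseline value is already collected for all four scores, so the plan may be giving up precision for nothing. Because the p-values are exploratory, what is at stake is the quality of the estimates and intervals.

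The text also needs reconciling. SAP 3.6 sits badly with a model that contains site, and section 5 does not record how the model departs from the protocol.

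**Working it through.** **Inputs.** From protocol 15.1 and SAP 3.1: 52 per arm, difference 3.9, SD of change 7.0, one-sided alpha 0.025, mean baseline EASI 14, mean changes −1.4 and −5.3. From protocol 6.2: baseline EASI 10–21. The documents give neither the baseline SD nor the slope, so both are assumed over a range.

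**1. The plan's own figure.** The SE of the difference is 7 × √(2/52) = 1.373, so the noncentrality is 3.9/1.373 = 2.84. The noncentral t on 102 df gives power 80.3%. The stated figure of more than 80% reproduces, and 104/0.8 = 130.

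**2. Range for the baseline SD.** With mean 14 and limits 10 and 21, the SD cannot exceed √((21−14)(14−10)) = 5.29, which needs all patients at the two limits. For a single-peaked distribution the largest variance comes from a point mass at 10 mixed with a uniform on 10–21: 11 × 8/3 − 4² = 13.33, an SD of 3.65. I take 2 to 3.65.

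**3. Slope.** If the planned reductions are proportional to baseline, the average slope of change on baseline is −(1.4/14 + 5.3/14)/2 = −0.24. The documents state mean reductions only, so proportionality is an assumption. A slope of −1.0 means follow-up is unrelated to baseline.

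**4. Power with baseline added.** r = slope × baseline SD/7, residual SD = 7 × √(1 − r²), 101 df.

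| Slope of change on baseline | Variance removed (r²), SD 2 to 3.65 | Power, SD 2 to 3.65 |
|---|---|---|
| 0 | 0% | 80.3% |
| −0.24 | 0.5–1.6% | 80.5–81.0% |
| −0.5 | 2.0–6.8% | 81.1–83.0% |
| −1.0 | 8.2–27.2% | 83.6–91.0% |

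In simulation (20,000 trials per scenario, baseline uniform on 10–21, follow-up slope 0, 0.5 or 1) both estimates were unbiased to about 0.01 points. One-sided type I error was 0.024–0.027 for both.

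**5. Chance imbalance.** At an assumed baseline SD of 3, one SE of baseline imbalance is 3 × √(2/52) = 0.59 points. It moves the unadjusted difference by 0.24 × 0.59 = 0.14 points, or 0.5 × 0.59 = 0.29 points. These are 0.10 and 0.21 of the SE of 1.373.

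**6. Missing visits.** With REPEATED, PROC GLM uses only patients who have every visit. At baseline SD 3 and slope −0.24, adjusted power is 80.8% with 52 per arm. If one patient per arm is seen at Day 28 but lost because of another missing visit, 51 per arm gives 80.0%. The whole gain is gone.

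**7. Treatment-by-site terms.** The SAP's three-way interaction puts treatment-by-site into the between-patient comparison. With k sites weighted equally, the variance of the difference is (49/k²) × Σ(1/a + 1/c), where a and c are the arm sizes at each site, on 104 − 2k df. The number of sites is not given. With equally likely sites, allocation not balanced by site and no gain from baseline, mean power is about 77% at 5 sites and 71% at 10. With perfectly equal cells only df are lost (94 or 84 instead of 102), and power is 80.3% or 80.2%. A site main effect alone costs at most 0.2 percentage points with 5 to 20 sites.

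**8. Other scores.** IGA has two eligible baseline values, VAS has an entry floor of 5, and Skindex 16 has no limit. None has a stated SD or slope. As an illustration for Skindex 16 only: with equal baseline and follow-up SDs and a correlation of 0.5 to 0.8 (all assumed), the variance of change falls by (1 − correlation)/2, which is 25% to 10%.

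**The case against.** The strongest case for leaving the plan alone is that it is valid, its power figure is right, EASI is secondary, the other scores are exploratory, and the only slope that can be tied to the documents adds 0.2 to 0.7 percentage points of power. All of that stands. It makes this an improvement worth making, not a defect. Two practical objections also stand. A covariate added to the planned PROC GLM model would inherit the loss of patients with a missing visit, and the treatment-by-site interaction could cost more than baseline gains. Both shape the fix. Neither argues against using baseline.

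Three stronger readings are tempting, and the documents do not support them.

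- A reader might infer that the unadjusted estimates are biased, or that the EASI entry limits make adjustment necessary. Randomization keeps the change-score comparison unbiased. Entry limits do not create the slope; they narrow the baseline range and so reduce the gain.
- A reader might expect a large gain, as the last row of the table could suggest. That row needs follow-up unrelated to baseline, and its top needs the widest single-peaked baseline distribution as well.
- A reader might infer that the SAP has abandoned the treatment-by-visit interaction because its model line lists only the three-way term. SAP 4.3.1 also says that the interaction of the within- and between-subject variables will be included. The text is unclear, not a demonstrated replacement.

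**Conclusion.** The concern holds as a missed, nearly free gain in precision. The planned analyses control type I error and are unbiased, and the sample size needs no change. The likely EASI gain is under one percentage point of power if reductions are proportional to baseline. It reaches 2.7 points at a slope of −0.5 with the widest assumed baseline SD (83.0 − 80.3), and is zero if the slope is 0. These figures rest on assumed baseline SDs of 2 to 3.65 and assumed slopes. They apply to a single-visit comparison with complete data and no site terms. No gain for IGA, VAS or Skindex 16 can be derived from the documents. SAP 3.6 and section 5 need rewording whatever the size of the gain.

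**What to change.** Before unblinding:

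- **Model (SAP 4.3.1 and 4.3.2).** For each score, estimate the treatment difference with its interval at Days 14, 28 and 42, with that score's baseline as a covariate. Use either a per-visit ANCOVA or a likelihood-based repeated-measures model with baseline-by-visit terms. Both keep a patient who was seen at the visit in question but missed another, which PROC GLM with REPEATED does not. The repeated-measures model should have treatment, visit and treatment-by-visit and, if wanted, a site main effect, but no treatment-by-site terms.
- **Main EASI estimate.** Name the baseline-adjusted Day 28 difference, which matches protocol 4.2 and the sample size. Keep the protocol's t-test as supportive.
- **SAP 3.6.** Say that the efficacy models for these four scores adjust for baseline, and for site if it is kept. Confine the sentence to the efficacy models, because SAP 4.2 separately compares age and BMI by ANCOVA.
- **SAP section 5.** Record the departures from protocol 15.4.5: the baseline covariate, any siteid terms, the dropped Baseline level of the within-subject factor, and the one-sided 95% interval in place of the 95% interval.

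The cost is about one degree of freedom per visit, extra rows in table families 14.2.1, 14.2.3, 14.2.5 and 14.2.8 (including their subgroup versions), and some reprogramming. No new data or patients are needed.

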### 3.7. Multiple Comparisons/Multiplicity

Analyses will not be adjusted for multiple endpoints.

### 3.8. Subpopulations

EASI, IGA, VAS, and Skindex 16 Scores will be reported separately for Black versus Non Black subjects, subjects  $\geq$  30 years versus < 30 years and male vs female subjects. Some of the parameters will also be presented by number of atopic dermatitis sites.

### 3.9. Withdrawals, Dropouts, Loss to Follow-up

Subjects who dropout after enrollment but prior to randomization will be replaced.

### 3.10. Missing, Unused, and Spurious Data

In general, there will be no substitutions made to accommodate missing data points. All data recorded on the case report form will be included in data listings that will accompany the clinical study report.

When tabulating adverse event data, partial dates will be handled as follows. If the day of the month is missing, the onset day will be set to the first day of the month unless it is the same month and year as study treatment. In this case, in order to conservatively report the event as treatment-emergent, the onset date will be assumed to be the date of treatment. If the onset day and month are both missing, the day and month will be assumed to be January 1, unless the event occurred in the same year as the study treatment. In this case, the event onset will be coded to the day of treatment in order to conservatively report the event as treatment-emergent. A missing onset date will be coded as the day of treatment.

In all cases, the resulting date will be compared to the AE end date, if present. If the imputed start date is later than the AE end date, then the start date will be set equal to the end date. The imputed start date is used only for determining treatment emergence; data listings will present the partial date as recorded on the CRF.

Missing AE severities will not be imputed and will be considered missing in any tabulations of AE severity. When relation of AEs to the study drug is missing, the AE will be considered "related" to study drug.

22

### 3.11. Visit Windows

It is expected that all visits should occur according to the protocol schedule. All data will be tabulated per the evaluation visit as recorded on the CRF even if the assessment is outside of the visit window. In data listings, the relative day of all dates will be presented.

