7.3 Study Withdrawal and Withdrawal From Investigational Product and Stopping Criteria

A participant may withdraw from the study at any time at his/her own request, or may be withdrawn at any time at the discretion of the Investigator.

Reasons for withdrawal (participants who refuse to complete any remaining study visits) or discontinuation (participants who prematurely stop the application) at any time during the study may include, but are not limited, to the following:

- For safety reasons, either at the discretion of the Investigator or at the participant's request
- For protocol violations at the discretion of AOBiome
- Due to concomitant therapy that could interfere with the results of the study (the Investigator will report all such information on the CRFs and decide, in accordance with AOBiome, whether the participant is to be withdrawn).

The reason for participant study withdrawal will be recorded in the electronic Case Report Form (eCRF). Data from participants withdrawing from the study will be considered evaluable up to the point at which they are withdrawn using the same criteria for evaluability as for participants who complete the study.

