8.14 Rescue Medications

Rescue medications will not be permissible in the trial should the study subject experience acute exacerbation of symptoms related to the treated disease. Subject may not start additional non-randomized medication and should immediately alert the study site PI. Subjects that need to start a rescue medication will be discontinued from the study and will be considered an Early Termination.

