11.6.7 Early Termination Visit

Every attempt should be made to complete all visits during the defined window periods. Subjects who do not complete all required study visits and withdraw from the study before Week 6 final visit, will be asked to complete the Early Termination Visit.

During the visit, the following will be obtained:

- record concomitant medications
- · physical exam
- Body weight
- obtain in clinic heart rate and blood pressure
- Oral hygiene questions
- EASI assessment
- VAS assessment
- Skindex 6 questionnaire
- IGA scoring assessment
- skin swab samples
- obtain study medication weight for Investigational Product compliance ((if ET visit occurs before Week 4 visit)
- blood for biomarkers (if ET visit occurs before Week 4 visit)
- blood for clinical chemistry and hematology (if ET visit occurs before Week 4 visit)
- return Investigational product (if ET visit occurs before Week 4 visit)
- return cleanser and moisturizer (if ET visit occurs before Week 4 visit)
- return Actigraphy watch (if ET visit occurs before Week 4 visit)
- return study diary (if ET visit occurs before Week 4 visit)
- AE Monitoring

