13.4 Subject Withdrawal Criteria

A subject may withdraw from the study at any time at his/her own request, or may be withdrawn at any time at the discretion of the Investigator for safety, behavioral, or administrative reasons.

Reasons for withdrawal (subjects who refuse to return for any remaining study visits) or discontinuation (subjects who prematurely stop the application) at any time during the study may include, but are not limited, to the following:

- For safety reasons, either at the discretion of the Investigator or at the subject's request
- For protocol violations at the discretion of AOBiome
- Due to concomitant therapy that could interfere with the results of the study (the Investigator will report all such information on the CRFs and decide, in accordance with AOBiome, whether the subject is to be withdrawn).

All premature discontinuations and their causes must be carefully documented by the Investigator on the CRF or if needed on the AE form.

If, for any reason, a subject is withdrawn before completing the final visit, the reason for termination will be entered on the CRF. All data gathered on the subject prior to termination will be made available to AOBiome. Subjects not completing the entire study should be fully evaluated when possible. The appropriate CRFs should be completed.

If the subject chooses to withdraw before completing the study, the subject should notify the study coordinator who will instruct the subject on completion of assessments for End of Study (EOS) visit Appendix A. For

subjects who refuse to complete the assessments for their early termination, every attempt must be made to check on their status, using any mode of communication such as telephone, email, fax, or text.

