### 1.2.2. Stopping Rules and Unblinding

A subject may withdraw from the study at any time at his/her own request, or may be withdrawn at any time at the discretion of the Investigator. Reasons for withdrawal (subjects who refuse to complete any remaining study visits) or discontinuation (subjects who prematurely stop the application) at any time during the study may include, but are not limited, to the following:

- $\overline{x}$  For safety reasons, either at the discretion of the Investigator or at the subject's request
- $\overline{x}$  For protocol violations at the discretion of AOBiome
- ☑ Due to concomitant therapy that could interfere with the results of the study (the Investigator will report all such information on the CRFs and decide, in accordance with AOBiome, whether the subject is to be withdrawn).

The reason for subject study withdrawal will be recorded in the electronic Case Report Form (eCRF). Data from subjects withdrawing from the study will be considered evaluable up to the point at which they are withdrawn using the same criteria for evaluability as for subjects who complete the study.

The Investigator may unblind a subject's treatment assignment only in the case of emergency or in the event of a serious medical condition when knowledge of the study treatment is essential for the appropriate clinical management or welfare of the subject, as determined by the Investigator. It is preferred (but not required) that the Investigator first contact the Medical Monitor to discuss options before unblinding the part subject's treatment assignment. The Investigator must notify the Sponsor as soon as possible when a subject's treatment assignment is unblinded without revealing the treatment assignment of the unblinded subject unless that information is deemed important for the safety of subjects currently in the study. The date and reason for the unblinding must be documented in the subject's study record.

The Medical Monitor may unblind the treatment assignment for any subject with a serious adverse event (SAE). If the SAE requires that an expedited regulatory report be sent to 1 or more regulatory agencies, a copy of the report, identifying the subject's treatment assignment, may be sent to clinical investigators in accordance with local regulations and/or sponsor policy.

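### Efficacy scores taken at the Early Termination visit have no assigned analysis visit and enter no planned between-arm test

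*SAP*

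**What the plan says.** **Collection.** Protocol 11.6.7 and Appendix A list EASI, VAS, Skindex and IGA at the ET visit, and SAP Table 1 repeats this. Subjects who miss required visits and "withdraw from the study before Week 6 final visit, will be asked to complete the Early Termination Visit". On rescue, Protocol 8.14 states: "Subjects that need to start a rescue medication will be discontinued from the study and will be considered an Early Termination".

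**Visit label.** SAP 3.11: "All data will be tabulated per the evaluation visit as recorded on the CRF even if the assessment is outside of the visit window". No rule moves a score from one visit to another.

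**Analysis.** SAP 4.3.1: "EASI, IGA, and VAS scores will be summarized using descriptive statistics at Baseline, Day 14, Day 28, and Day 42". The mixed model has "one within-subject variable (Day 14, Day 28, and Day 42". The t-tests and improvement proportions use the same three post-baseline days. SAP 4.3.2 summarises Skindex at those days and applies a similar mixed model. No last-assessment endpoint is defined, and SAP 3.9 covers only subjects lost before randomization.

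**A second route for withdrawals.** Under Protocol 13.4, a subject who chooses to withdraw notifies the study coordinator, who "will instruct the subject on completion of assessments for End of Study (EOS) visit Appendix A". In the schedule, EOS is the Week 6, Day 42 visit.

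**Evaluability.** Protocol 7.3: "Data from participants withdrawing from the study will be considered evaluable up to the point at which they are withdrawn". SAP 1.2.2 says the same. Both sentences go on to apply the evaluability criteria used for completers.

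**The concern.** The trial pays to measure every efficacy scale when a subject leaves, then names no analysis that uses the result. A subject who flares and leaves on Day 26 has a measured EASI, but is blank at Day 28 if the form says ET. A completer seen well outside the window still counts as Day 28 if the form says so. The label decides, not the study day.

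Subjects who need rescue are ended as Early Terminations, so the omitted scores may include many of the worse outcomes. The ITT population is all randomized subjects, but its Day 28 comparison contains only those with a visit labelled Day 28. The SAP's per-protocol population requires a Day 28 visit, so it cannot reveal the effect of those who left.

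The two protocol routes add a second problem. The same withdrawal in week 3 could be left out of the comparisons (recorded as ET) or placed at Day 42 (recorded as EOS).

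**Working it through.** **1. Where an ET score can go**

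| Planned output | Visits named | Score labelled ET | Score labelled EOS |
|---|---|---|---|
| Descriptive summaries (SAP 4.3.1, 4.3.2) | Baseline, Days 14, 28, 42 | Not named; shells say to repeat for all visits, so a row is possible | Day 42 |
| Mixed model | Days 14, 28, 42 | No | Day 42 |
| t-tests | Days 14, 28, 42 | No | Day 42 |
| Shift tables (shell 14.2.2.1) | Post-baseline visits, with a missing column | Missing at the scheduled visit | Day 42 |
| Improvement proportions (shell 14.2.7.1) | Days 14, 28, 42 | No | Day 42 |
| Listing 16.2.6.1 | All recorded data | Yes | Yes |

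**2. The plan's own figures** (Protocol 15.1, SAP 3.1)

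Inputs: 52 per arm, changes of -1.4 (vehicle) and -5.3 (active), SD 7.0, one-sided alpha 0.025, 20% dropout.

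- Difference: -1.4 - (-5.3) = 3.9.
- Noncentrality: 3.9 / (7 × √(2/52)) = 2.84 on 102 df. Power is 0.803 (0.811 by the normal approximation), which reproduces the stated figure of over 80%.
- Randomized: 104 / 0.8 = 130.

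**3. How many subjects**

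130 - 104 = 26, or 13 per arm if loss is equal. This is a ceiling: it assumes that every dropout leaves before Day 28 and attends the ET visit.

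**4. Information left out**

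If a fraction r of those 13 per arm had an ET score usable at Day 28, n per arm = 52 + 13r. With the effect and SD unchanged:

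| r | 0 | 0.25 | 0.50 | 0.75 | 1 |
|---|---|---|---|---|---|
| n per arm | 52 | 55.25 | 58.5 | 61.75 | 65 |
| Power | 0.803 | 0.827 | 0.848 | 0.867 | 0.883 |

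**5. Bias, as illustration only**

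The documents give no leaver scores and no dropout by arm. Everything below about leavers is assumed, with the same leaver change in both arms.

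*Reading A: -1.4 and -5.3 are the completers' means.* All-randomized mean = (1 - p) × completer mean + p × c, where p is the loss and c the leavers' change, taken from -1.4 to +4.

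- Loss 20%/20%: 0.8 × 3.9 = 3.12 for any c.
- Loss 30% vehicle, 10% active: (-0.98 + 0.3c) - (-4.77 + 0.1c) = 3.79 + 0.2c, from 3.51 to 4.59.
- Loss 10% vehicle, 30% active: (-1.26 + 0.1c) - (-3.71 + 0.3c) = 2.45 - 0.2c, from 2.73 down to 1.65.

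The completers' comparison shows 3.9 in every case, so it can be too high or too low.

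*Reading B: -1.4 and -5.3 are the all-randomized means.* Stayers' mean = (M - p × L) / (1 - p), where M is the arm mean and L the leavers' change.

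- Loss 30% vehicle, 10% active, L = +2: vehicle (-1.4 - 0.6)/0.7 = -2.86; active (-5.3 - 0.2)/0.9 = -6.11; difference 3.25. Power with 45.5 and 58.5 subjects is about 0.64.
- Same loss, L = +4: -2.6/0.7 = -3.71 and -5.7/0.9 = -6.33; difference 2.62.
- Loss 20%/20%, L = +2: -1.8/0.8 = -2.25 and -5.7/0.8 = -7.125; difference 4.88.

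Here too the shift goes both ways around 3.9.

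**The case against.** Several stronger readings are tempting, and the documents do not support them.

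- *That ET scores are shut out of every efficacy table.* SAP 3.11 promises to tabulate all data by recorded visit, ET is a visit column in SAP Table 1, and the summary shells are to be repeated for all visits. A descriptive ET row is open. The SAP is silent, not prohibitive. What stands is that no test is planned on it.
- *That the last score of every early stopper is lost.* Protocol 7.3 separates stopping application from leaving the study, and those who keep attending are tabulated normally. Some leavers will refuse the ET visit, so their last score may be a Day 14 value, which is used. Those who leave after Day 28 already have the endpoint score. A score recorded as EOS enters as Day 42.
- *That the plan contradicts its own statement on evaluability.* "Data from subjects withdrawing from the study will be considered evaluable up to the point at which they are withdrawn" continues by applying the completers' criteria, and completers are assessed at scheduled visits. It does not promise that an ET score counts as Day 28.
- *That a bias of known size follows.* The figures in step 5 depend on assumed leaver values and, in most cases, on assumed unequal loss. The 3.12 and 4.88 at equal loss arise because leavers are given the same change in both arms, that is, no treatment effect. That rescue users dominate the leavers is an inference from Protocol 8.14; no breakdown by reason is given.

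Two further objections have weight. Putting an ET value in place of Day 28 resembles carrying the last observation forward, while Protocol 15.4.6 and SAP 3.10 rule out imputation and substitution. An added row must therefore be presented as a measured last assessment. Also, EASI is a secondary objective, the other scales are exploratory, and Protocol 15.4.5 treats efficacy p-values as exploratory. This limits the consequence but does not remove the gap.

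**Conclusion.** The point holds in this form. ET efficacy scores are scheduled, but a score labelled ET has no analysis visit and enters no planned between-arm test. The ITT Day 28 comparison rests on subjects with a visit labelled Day 28. A withdrawal recorded as EOS would be tabulated as Day 42 regardless of its actual day.

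At the planned dropout, at most 26 of 130 subjects are affected. Using every one of those scores at Day 28 would raise nominal power from about 80% to about 88%, if the effect and SD stayed the same. The direction and size of any bias cannot be determined from the documents. That uncertainty is a reason to fix the rule before unblinding. The change is worth making because it is cheap; the primary safety objective is not touched.

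**What to change.** 1. **Protocol 11.6.7 and 13.4.** Reconcile which visit label an early withdrawal assessment carries, so that it is not tabulated as Day 42 unless taken near Day 42.
2. **SAP 3.11.** Assign an ET efficacy score by actual study day to a scheduled visit only if it falls in a stated window around that visit and the visit has no value. Scheduled visits are 14 days apart, so a half-width below 7 days avoids overlap. Leave very early ET scores unassigned: calling a score from the first days Day 14 would misstate exposure.
3. **SAP 4.3.1, 4.3.2 and the matching table shells.** Add one supportive row, last on-treatment assessment: the Day 28 value, or the ET value if the subject left before Day 28. Use the same between-arm t-test, and label the row as measured data, not as an imputed Day 28 value.

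The cost is SAP wording, one derived visit variable, one extra row per table, and the protocol clarification. Some ET scores reflect fewer than 28 days of treatment, so the row is supportive only.

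The fix reaches the summaries, t-tests, shift tables and improvement proportions. It does not bring most early leavers into the mixed-model test, because PROC GLM with REPEATED drops any subject lacking one of the three post-baseline values.
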